## 7. CORRELATIVE/SPECIAL STUDIES

### 7.1 Pharmacodynamic Studies

#### **PBMCs:**

Relationships between entinostat and aldesleukin exposure and pharmacodynamic effects (e.g. histone acetylation in peripheral blood mononuclear cells or PBMCs and changes in T cell subset population) will be characterized.

Collect four 8 ml of peripheral blood in CPT tubes for mononuclear cell fraction. Mononuclear cell fractions will be obtained in CPT tubes (Beckon Dickinson) sodium citrate using manufacture's guidelines.

Collection time points will be:

- Prior to treatment on Day -14 and Day-7,
- Cycle 1 – pre-dose on Day 1 and at 8 hrs. and 24 hrs. after the dose of entinostat,
- Cycle 1 - pre-dose Day 15
- Cycle 2 and 3 - pre-dose Day 1
- Cycle 2 and 3 - pre-dose Day 15
- At the time of progression.

Samples will be processed, PBMCs isolated and histone acetylation status determined. Blood samples will be also analyzed for immune cell sub populations. CD4+, CD4+/Foxp3, CD8+ cells, NK cells will be quantitated by FACS analysis. Foxp3 gene expression will be evaluated by quantitative RTPCR. Specimens must be shipped at ambient temperature.

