## **7.2 Pharmacokinetic studies (Phase I only)**

Pharmacokinetic analysis will be performed by [name], PhD. at the Analytical Pharmacology Core Laboratory at the SKCCC at Johns Hopkins. Patients in the phase I component of the study will have plasma samples collected to assess entinostat pharmacokinetics. Entinostat concentrations will be assessed pretreatment on Day -14 and at 2 and 6 hrs., Day -7, pretreatment on Day 1 and at 2 and 6 hrs. and Day 15 during the first cycle and at the time of progression. These pharmacokinetic parameters will be used to explore the relationship between entinostat exposure with pharmacodynamic (PD) endpoints such as toxicity and histone acetylation in peripheral blood mononuclear cells or PBMCs and changes in T cell subset populations.

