#### Shipment of Paraffin-embedded Tissue

**Notification of sample shipment should be sent by email to**

**[name] and [name] at [[contact]](mailto:[contact]) and [[contact]](mailto:[contact]).**

#### Analysis

These samples will be analyzed for microvessel density (anti-CD34 staining), HIF-1  $\alpha$  staining, acetylated Histone and CD4+/FOXP3+ T cells. All IHC studies will be done with established protocols in [name] lab.

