### 7.4.2 Optional fresh tumor samples

#### Sample Collection

- Optional tumor biopsy samples will be collected from patients with accessible tumor per institutional procedure.

- The specific biopsy samples and time points for collection of fresh tumor samples are given below:

Time Points	Number of Tumor Biopsy Samples per Time Point
Pretreatment	1
On treatment *	1

\* The on-treatment samples will be collected 2 hours following the most recent dose of entinostat on Day 30 Cycle 1 +/- 2 days. To ensure that these samples are obtained at the correct time, patients are urged to take their entinostat dose in the clinic on the day of on-treatment sample collection. The time of the entinostat dose and sample collection must be recorded.

Attn: [name]

Laboratory of [name]  
Division of Hematology and Oncology,  
Department of Medicine,  
Indiana University School of Medicine  
[name]  
[name]  
Indianapolis, IN 46202

Notification of sample shipment should be sent by email to  
[name] and [name] at [[contact]](mailto:[contact]) and [[contact]](mailto:[contact]).

These samples will be also analyzed for microvessel density (anti-CD34 staining), HIF-1  $\alpha$  staining, acetylated histone, CD4+, CD4+/FOXP3+, and CD8+ T cells. All IHC studies will be done with established protocols in [name] lab.

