**NCI Protocol #: 7870**

parameters on time-to-event outcomes.

Logistic regression will be used to explore the relationship between entinostat exposure (plasma concentrations) with pharmacodynamic (PD) endpoints (e.g., toxicity and histone acetylation in peripheral blood mononuclear cells and change in T cell subset population).

We will determine if initial levels of specific T lymphocytes (Tregs) or changes in the level of specific T lymphocytes from baseline might predict for response to this combination therapy. In this study Tregs are defined as CD4+CD25hi T cells. The hypotheses are that low baseline levels of Treg would be associated with an increased probability of response and that decreasing Tregs from baseline would be associated with an increased probability of response. Continuous baseline values of Treg (expressed as a frequency) and the change in Treg from baseline (4 weeks post treatment – pretreatment) as well as binary versions of these variables will be explored for an association with response. A 30% decrease from baseline will be used as the binary cutpoint for Treg change.

Two PET-derived indices of glucose metabolism: Standard Uptake Value (SUV) and FDG influx rate constant (Ki) will be used to determine whether early changes in tumor metabolisms by FDG PET/CT scan anticipate anatomic changes in patients receiving the combination of entinostat and IL-2. These two parameters will be measured at baseline and at week 5 using identical PET/CT acquisition protocols. Continuous change from baseline and binary (30% decrease from baseline) measures of these predictors will also be explored for an association with response. The hypothesis for these predictors is that treatment would decrease glucose metabolism, increasing response.

Data analysis for Treg and PET correlative studies:

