This study will provide estimates of means and standard deviations for baseline Treg, change in Treg at week four and changes in the PET glucose metabolism indices at week five. Transformations of these predictors will be considered before analyses. For each endpoint, we will determine how well the responders and non-responders are distinguished. For binary predictors, the sensitivity and specificity with 95% confidence intervals will be reported. T tests will be used to compare the mean change between responders and non-responders. If there are sufficient numbers of responders, partial responders and non-responders an ANOVA will be used to compare changes in these three groups. If complete data are obtained for CD4+CD25hi T cells at multiple time points post treatment, repeated measures ANOVA will be performed to evaluate data for trends over time.

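### Section 11.3 defines Tregs as CD4+CD25hi, but the blood FACS list in Section 7.1 names CD4+/Foxp3 and not CD25, so the listed assays do not yield the prespecified Treg predictor; separately, the exposure analysis applies logistic regression to continuous outcomes

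*Combined protocol and SAP*

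**What the plan says.** **Analysis section.** In the secondary objectives of Section 11.3 the definition is explicit: "In this study Tregs are defined as CD4+CD25 hi T cells". Under that heading the plan examines baseline Treg frequency and change from baseline against response. It adds a binary version: "A 30% decrease from baseline will be used as the binary cutpoint for Treg change". The paragraph on data analysis for the Treg and PET correlatives repeats the marker when it plans repeated-measures ANOVA: "If complete data are obtained for CD4+CD25 hi T cells at multiple time points post treatment".

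**Assay section.** For blood, Section 7.1 says "CD4+, CD4+/Foxp3, CD8+ cells, NK cells will be quantitated by FACS analysis" and adds quantitative RT-PCR for Foxp3. The paraffin list in Section 7.4.1 ends with "acetylated Histone and CD4+/FOXP3+ T cells", and the fresh-tissue list in Section 7.4.2 with "acetylated histone, CD4+, CD4+/FOXP3+, and CD8+ T cells". The study calendar shows pharmacodynamic samples without naming markers.

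**Exposure analysis.** Section 11.3 also says "Logistic regression will be used to explore the relationship between entinostat exposure (plasma concentrations) with pharmacodynamic (PD) endpoints", giving toxicity, histone acetylation and change in T-cell subsets as examples. Section 7.2 limits the sampling: "Patients in the phase I component of the study will have plasma samples collected to assess entinostat pharmacokinetics".

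**The concern.** A prespecified predictor should be traceable to a listed measurement. Here the analysis section names one cell population and the assay section another. If CD25 is stained, Section 7.1 is incomplete. If it is not, the Treg predictor in Section 11.3 will not exist and something must replace it. A replacement chosen after markers have been set against response would be post hoc, in an analysis for which the plan states directional hypotheses, a cutpoint, sensitivity and specificity, and t tests.

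The exposure analysis has a separate fault. Logistic regression needs a categorical outcome. Toxicity can be coded as binary; histone acetylation and subset change are continuous as the plan describes them. An analyst would have to invent a cut or change the model.

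**Working it through.** Most of this check is textual.

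**1. Marker required against marker listed.**

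| Place | Population named | CD25 named? |
|---|---|---|
| 11.3, Treg definition | CD4+CD25hi | yes |
| 11.3, repeated measures | CD4+CD25hi | yes |
| 11.3, general baseline associations | CD4+, CD4+/Foxp3, CD8+ | no |
| Objective 1.3.4 | CD4+, CD8+, CD4+/Foxp3 | no |
| 7.1, blood FACS | CD4+, CD4+/Foxp3, CD8+, NK | no |
| 7.1, blood RT-PCR | Foxp3 | no |

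The comparison that matters is with the blood list, because only blood is sampled serially. Outside Section 11.3, CD25 appears only in the mouse work in Section 2.5.

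**2. Whether one marker can stand in for the other.** Section 2.5 reports that, in lymph nodes of mice given the combination, the CD4+25+ percentage rose and the Foxp3+ percentage fell. It then describes fewer regulatory T cells, which matches the Foxp3+ direction. The hypothesis in 11.3 is that falling Tregs go with response, so the choice of marker could change the apparent direction. Mouse lymph node and CD25+ are not human blood and CD25hi. The data are a reason to settle the marker in advance; they do not show which is right.

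**3. Draws that use this blood list (7.1).** Day -14 and Day -7: 2. Cycle 1 Day 1 pre-dose, 8 h and 24 h: 3. Cycle 1 Day 15: 1. Cycles 2 and 3, Day 1: 2. Cycles 2 and 3, Day 15: 2. Progression: 1. Total 2 + 3 + 1 + 2 + 2 + 1 = 11 at most per patient.

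**4. The four-week value.** Section 11.3 takes the change at four weeks after treatment without naming a draw or an anchor.
- Counted from first entinostat on Day -14 (no Day 0 assumed): 14 days to Day 1 plus 14 to Day 15 = 28 days. But the calendar places Day 15 in Week 3, and its footnote lets that course start up to 7 days late.
- Counted from aldesleukin Day 1: 1 + 28 = Day 29. Section 7.1 has no blood draw between cycle 1 Day 15 and cycle 2 Day 1 apart from progression.

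**5. Outcome type in the exposure analysis.** Toxicity: binary, logistic regression fits. Histone acetylation: no cutpoint anywhere. T-cell subset change: the only cut is 30% for Treg change, which 11.3 gives for the response analysis.

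**6. Size of the exposure analysis.** The documents give no Phase I total. Section 4.1 says 5 mg (level 2) became the recommended dose, and 11.2 opens level 2 when level 1 has no DLT. Assume 3 or 4 patients at level 1 (the text gives only a minimum of 3). Level 2 takes 3 or 4, plus another 3 or 4 after one DLT, so 3 to 8. Total: 3 + 3 = 6 to 4 + 8 = 12.

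As a yardstick only, since the plan proposes no such test, the smallest Pearson correlation significant at two-sided 0.05 is r = t / √(df + t²):
- n = 6: df = 4, t = 2.776, r = 2.776 / √(4 + 7.706) = 0.81
- n = 12: df = 10, t = 2.228, r = 2.228 / √(10 + 4.964) = 0.58

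**The case against.** The best defence is that the plan has one clinical definition of Treg, used consistently, and an assay list that is merely short. Section 7.1 speaks broadly of immune cell subpopulations and does not call its list exhaustive. Blood collection and FACS are already planned, so a CD25 stain may well be part of the panel. This stands: a reader might infer that the Treg analyses cannot be run, or that CD25 was never stained, and the documents support neither. They show only that the list does not name the marker.

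It is also fair that objective 1.3.4 is served without CD25, because 11.3 separately relates baseline CD4+/Foxp3 to response and survival. That limits the damage but does not supply the change, 30%-cut or repeated-measures analyses as defined.

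A reader might count the tissue lists as further panels lacking CD25. That would pad the case. Paraffin blocks are pre-dosing only, and fresh biopsy is optional and limited to pretreatment and Day 30, so neither could supply the serial measure.

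On the exposure analysis, logistic regression does suit toxicity, and the 30% cut could be borrowed for Treg change. The plan does not say so, and histone acetylation would still have no cut.

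**Conclusion.** The point holds as a mismatch between Section 11.3 and the blood assay list in 7.1. The prespecified Treg predictor cannot be traced to a listed measurement. Its scope is exploratory correlatives; the response endpoint, the 36-patient sample size and the error rates are untouched. No effect size is available. The post hoc risk depends on two facts the documents do not settle: whether CD25 is stained, and whether markers have already been compared with response.

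The model mismatch also holds for histone acetylation and, as written, for T-cell subset change. With roughly 6 to 12 Phase I patients the analysis can only be descriptive. That range is an assumption: level 1 has no stated upper limit, and 11.7.2 replaces non-evaluable patients.

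A reader might take the four-week Treg value to be the cycle 1 Day 15 draw. The 28-day count makes that possible, but no text says it. The Week 3 label, the permitted delay and the alternative anchor of aldesleukin Day 1 (used in Appendix A for the PET scan) leave it open. The finding is only that the draw is unnamed.

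**What to change.** 1. Use one Treg definition in 7.1 and 11.3, settled before marker data are compared with response.
   - If CD25 is stained: add CD4+CD25hi to the FACS list in 7.1, keep it as the prespecified predictor, and report CD4+/Foxp3 alongside.
   - If it is not: restate the Treg analyses in 11.3 as CD4+/Foxp3 by amendment.
   - If markers have already been compared with response: label the choice post hoc.
2. For entinostat exposure, use linear regression or rank correlation for histone acetylation and T-cell subset change. Keep logistic regression for binary toxicity. State the Phase I n and call the analysis descriptive.
3. Ask the sponsor to name the draw that supplies the four-week Treg value and the date from which it is counted.

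The cost is wording in 7.1 and 11.3, plus an amendment if the marker changes. Items 1 and 2 need no new samples; item 3 asks only for a clarification.

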### **Baseline documentation of “Target” and “Non-Target” lesions**

- All measurable lesions up to a maximum of five lesions per organ and 10 lesions in total, representative of all involved organs should be identified as *target lesions* and recorded and measured at baseline.
- Target lesions should be selected on the basis of their size (lesions with the longest diameter) and their suitability for accurate repeated measurements (either by imaging techniques or clinically).
- A sum of the longest diameter (LD) for *all target lesions* will be calculated and reported as the baseline sum LD. The baseline sum LD will be used as reference by which to characterize the objective tumor.
- All other lesions (or sites of disease) should be identified as *non-target lesions* and should also be recorded at baseline. Measurements of these lesions are not required, but the presence or absence of each should be noted throughout follow-up.

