### 11.3 Phase II

#### Primary Objective:

Once a recommended dose has been determined in the Phase I portion of the study, the cohort will be expanded so that 36 new patients will be treated at this dose level. The primary objective of this phase is to evaluate the safety and efficacy of the combination of entinostat and IL-2. The primary endpoint is overall response rate (complete plus partial). Enrollment is expected to be

between 1 and 2 patients per month. The combination treatment will be considered unsuccessful if the response rate is 20% or less, and it will be considered active enough to pursue further if the response rate was 40% or greater. To test this hypothesis, the fixed sample size for a single-stage study with a type I error of 10% and a type II error of 10%, based on an exact binomial test, is 36. If 11 or more of the patients have a response, the hypothesis that the response rate is  $\leq 20\%$  is rejected with a target error rate of 0.10. This design has type I and type II errors of 0.09 and 0.09, respectively.

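### The PET analysis asks whether early metabolic change anticipates anatomic change, but relates PET only to response category and never to the measured change in tumour size

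*Combined protocol and SAP*

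**What the plan says.** Section 11.3 (Phase II, Secondary Objectives) states the PET question in anatomic terms: SUV and Ki, measured at baseline and week 5, "will be used to determine whether early changes in tumor metabolisms by FDG PET/CT scan anticipate anatomic changes". The same paragraph then says that continuous change and a 30% decrease in each index will be explored for association with response. The data-analysis paragraph for the Treg and PET studies adds: "For each endpoint, we will determine how well the responders and non-responders are distinguished". Its tools are sensitivity and specificity for binary predictors, t tests of mean change between responders and non-responders, and an ANOVA over responders, partial responders and non-responders if there are enough of each.

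Tumour size is already collected. Section 9.1 has the longest diameters of all target lesions summed at baseline: "The baseline sum LD will be used as reference by which to characterize the objective tumor". Section 9.2.1 derives partial response and progression from change in that sum. Sections 4.1, 8 (footnote 4) and 9 schedule tumour assessment at week 11 of each cycle. No analysis in section 11.3 uses the change in that sum as an outcome.

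**The concern.** A question about anatomic change is answered with a category. Under the response cut, a patient whose target lesions shrink by 29% counts the same as one whose disease progresses. Elsewhere the protocol treats the lesser shrinkage as meaningful: section 4.1 distinguishes stable disease with and without shrinkage when deciding on further cycles, and section 11.1 warns that response rate may not capture all of the added immune effect.

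At the design's response rates of 20% to 40%, 36 patients give about 7 to 14 responders (0.20 × 36 = 7.2; 0.40 × 36 = 14.4). Appendix A hopes that PET may predict response ahead of anatomic assessment and help select patients for further aldesleukin. A marker that tracks tumour size moderately well could go unrecognised when judged only by a small responder group.

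**Working it through.** **Inputs from the plan (section 11.3).** Sample size: "36 new patients will be treated at this dose level". Response rates: "The combination treatment will be considered unsuccessful if the response rate is 20% or less", and "active enough to pursue further if the response rate was 40% or greater". Decision rule: "If 11 or more of the patients have a response".

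**Assumed, because the plan does not state them.** Two-sided alpha 0.05; marker-to-size correlation 0.3 to 0.5; bivariate normality; response treated as the best-shrinking fraction of patients, 31% in the main comparison (11/36 = 30.6%).

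**Step 1. The plan's own figures.** With X binomial on 36 patients, P(X ≥ 11) at a rate of 0.20 is 0.0889, and P(X ≤ 10) at 0.40 is 0.0904. Both round to the stated 0.09, so the primary design reproduces. There is no corresponding figure for the PET or Treg analyses.

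**Step 2. Question against outcome.**

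| Marker | Stated question | Planned outcome | Match? |
|---|---|---|---|
| PET change (SUV, Ki) | anatomic change | response category | no |
| Treg, baseline and change | response | response category | yes |

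**Step 3. Information kept when a normal outcome is cut at proportion p.** Efficiency = φ(z_p)² / [p(1 − p)].

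- p = 0.20: 0.2800² / 0.16 = 0.49, so 36 patients act like about 18.
- p = 0.30: 0.3477² / 0.21 = 0.58, like about 21.
- p = 0.40: 0.3863² / 0.24 = 0.62, like about 22.

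**Step 4. Three-group ANOVA.** At correlation 0.4, assuming 6% complete responses, simulated power is 32%, 40% and 44% at response rates of 20%, 30% and 40%. The two-group t test gives 38%, 45% and 48%. The extra category does not recover the loss.

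**Step 5. Spearman on size change against the responder t test** (simulation; n = 36, 31% responders, size change available for all).

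| Correlation | Spearman | t test | Gain (points) |
|---|---|---|---|
| 0.3 | 40% | 27% | 13 |
| 0.4 | 62% | 44% | 18 |
| 0.5 | 83% | 65% | 18 |

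These are good to a point or two. With 25 patients and correlation 0.4, the figures are 47% vs 33%.

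**Step 6. Effect of worst ranks for early failures.** At correlation 0.4, with 20% to 40% of patients worst-ranked:

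- If they truly have the worst size change, Spearman power stays at about 57% to 63%.
- If they are spread at random among non-responders, it is 48% (20% worst-ranked) or 40% (40% worst-ranked), against 44% for the t test.
- With 40% at random, it is 23% vs 26% at correlation 0.3, and 59% vs 66% at 0.5.

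**Step 7. How many might be worst-ranked?** Take the constant failure rates in section 11.3 and 11 weeks = 11/52 year. At the historical 2.77 per person-year, 1 − exp(−2.77 × 11/52) = 1 − exp(−0.586) = 44% would have progressed or died. At the hoped-for 1.85, 1 − exp(−0.391) = 32%. A share near 40% is therefore plausible. How much of it would be unrelated to target-lesion size cannot be known from the documents.

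**The case against.** The strongest reply is that these analyses are exploratory, carry no power claim and leave the primary endpoint untouched, so nothing stated is wrong. That stands, and it limits the weight of the point.

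Several stronger readings are tempting but are not supported:

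- **The same mismatch affects Treg.** It does not. Section 11.3 frames both Treg hypotheses in terms of the probability of response, so response is the right outcome there. Only the efficiency argument carries over.
- **Everything is tested only as response yes/no.** Too strong. The conditional ANOVA has three groups, objective 1.3.4 names toxicity and survival among the outcomes for tumour metabolism, and logistic and Cox models are specified for baseline laboratory parameters. None of these uses tumour size, however.
- **The plan gives away about a third of its power.** That figure depends on an unstated correlation, alpha and response rate. Comparing a Pearson test on complete normal data with the t test at n = 36, the relative loss runs from 3% to 47% over correlations 0.2 to 0.7 and response rates of 20% to 40%. Step 6 shows that a worst-rank rule can remove the gain.
- **Week-11 size should replace response as the main analysis.** Sections 9.2.3 and 9.2.4 define best overall response, with confirmation at least four weeks later and with non-target and new lesions counted. Section 4.1 allows up to three cycles. Response is thus not a cut of week-11 size, and replacing it would lose later responses and depart from the primary endpoint.

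**Conclusion.** The point holds for PET as a missed analysis, not as an error in any stated figure. The stated question concerns anatomic change, the planned outcome is response category, and a direct size measure is already collected.

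The likely benefit is 13 to 18 points of power at correlations of 0.3 to 0.5. This assumes 36 patients with complete data, 31% responders, two-sided 5%, bivariate normality, and response approximated by a cut of size change. It falls to nil or slightly below if about 40% of patients are worst-ranked for reasons unrelated to target-lesion size. The actual number analysed will be below 36: section 3.1.3 admits patients with evaluable disease only, and Appendix A limits the PET sub-study to lesions of about 1 cm or more. This is a low-priority improvement. The case for it rests more on answering the plan's own question than on any one power figure.

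**What to change.** Add to section 11.3, for PET only, a pre-specified additional analysis: the Spearman rank association of week-5 change in SUV and in Ki with percent change in the sum of longest diameters from baseline to the week-11 scan, in patients with measurable target lesions and both PET scans. Report it twice: once with patients who died or progressed (including by new lesions) before or at that scan given the worst rank, and once using observed size change only. The difference shows how far the result depends on the ranking rule. Keep the responder comparisons as planned. Leave response as the Treg outcome; size change may be added there as supplementary.

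The cost is a few sentences, with no new scan, visit or patient. The plan must also state a rule for patients who have no week-11 measurement for other reasons, and report how many patients drop out because they have evaluable-only disease or no PET-suitable lesion.
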